magnesium, and phosphorus. Creatinine clearance (CrCl) will be conducted at screening only; Calculation of CrCl will be based on acceptable institution standard).

- g. Screening laboratory may be used if conducted within 3-7 days of CID1.
- h. Chemistry will be conducted **every week** for the first 3 cycles and then **every 2 weeks**, with the exception of liver function tests (AST/ALT/ALP/bilirubin) which will be done **weekly until week 32**, and then **every 2 weeks** thereafter.
- i. Coagulation factors will be done on Day 1 of every other cycle (e.g., C3D1, C5D1...).
- j. Urinalysis (specific gravity, pH, glucose, protein, ketones, and blood) performed at Screening and as clinically indicated.
- k. In the event of possible abnormal ECG findings, per the discretion of the investigator, additional ECG reads could be added at follow-up visits. The ECG evaluation will be performed centrally. Clinically significant ECG abnormalities will be recorded on the eCRF. Triplicate ECGs, at least 3 minutes apart, will be performed if QTcF is > 500 msec or if the Investigator identifies an ECG finding (for example QT interval prolonged or cardiac arrhythmia) that is an adverse event and related to investigational product.
- l. Pre-menopausal female patients of childbearing potential only. Urine or serum pregnancy tests are acceptable.
- m. CT or MRI with contrast, of the neck, chest, abdomen, and pelvis are acceptable (PET/CT is not allowed for study assessments, unless CT is done with IV contrast). Images will be repeated every 8 weeks ( $\pm 3$  days) during treatment period until disease progression. During the Long-term Follow-up visit, only in patients who discontinued investigational product due to toxicity, radiographic imaging will be done every 3 months until disease progression or until patient initiates another anti-cancer therapy. The same radiographic technique of each region must be used consistently throughout the study. Refer to Imaging Manual. A repeat of tumor imaging will be required for the purposes of confirmation of response (i.e., partial response, and/or complete response). The confirmation scan should be no earlier than 4 weeks following the first indication of response.
- n. Quality of life questionnaire will be administered every 4 weeks before investigational product administration or receipt of radiological imaging results

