6.4.1.2 Secondary Efficacy Variables

Secondary efficacy endpoints include the following:

Duration of Response (DOR): defined as the time interval from the initial confirmed response of CR or PR to the earlier of the first documentation of disease progression (per RECIST v1.1 or modified MDA criteria) or death from any cause, as determined by Investigator review. DOR will be calculated in months as (date of disease progression or death/censoring – date of initial response + 1) / 30.4375.

For DOR (and PFS) the date of progression or death and censoring will be based on the Food and Drug Administration (FDA) guidance *Clinical Trial Endpoints for the Approval of Cancer Drugs and Biologics* (May 2007), as defined in Table 7.

Table 7 Determining Date of Progression or Censoring for PFS and DOR Analysis

Situation	Date of Progression or Censoring	Outcome
Alive and without documentation of disease progression.	Date of last disease assessment. All patients still alive and without documentation of disease will be censored as of July 31, 2022.	Censored
Treatment discontinuation for undocumented progression	Date of last disease assessment	Censored
Treatment discontinuation for toxicity or other reason	Date of last disease assessment	Censored
Other anticancer treatment started before documentation of disease progression or death	Date of last disease assessment prior to start of other anticancer treatment	Censored

Death before first disease assessment	Date of death	Progressed
Death or disease progression between planned disease assessments	Date of death or first disease assessment showing disease progression, whichever occurs first	Progressed
Death or progression after more than one missed disease assessment	Date of last disease assessment visit without documentation of disease progression that is before the first missed visit	Censored

As part of the sensitivity analysis, DOR will also be derived as follows:

- As above but where confirmation of PR/CR is not required.
- As above but based on central review rather than Investigator review.
- As above but based on central review rather than Investigator review and where confirmation of PR/CR is not required.

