Progression-Free Survival (PFS): defined as the interval from the start of investigational product to the earlier of the first documentation of disease progression (per RECIST v1.1 or modified MDA criteria) or death from any cause, as determined by Investigator review. Progression-free survival will be defined in months as: (date of progression or death/censoring – date of first infusion + 1) / 30.4375.

Patients without disease progression or death will be censored as per Table 7.

As part of the sensitivity analysis, PFS will also be derived as follows:

- As above but based on central review rather than Investigator review.

Overall Survival (OS): defined as the time from the date of start of treatment to the date of death from any cause. Subjects with no documentation of death will be censored at the last date known to be alive, per the data collection. Sites will be asked to search public registries for any possible death dates for subjects who withdrew consent from the study (as per FDA Guidance for Sponsors, Clinical Investigators, and IRBs

Data Retention When Subjects Withdraw from FDA-Regulated Clinical Trials). Where it is possible for this search to be done, any deaths found will be included in the analysis. Overall survival time will be calculated in months as (date of death/censoring – date of first infusion + 1) / 30.4375.

As part of the sensitivity analysis, OS will also be derived as follows:

- As above but where date of first diagnosis of recurrent or metastatic disease is used instead of date of first infusion.
- As above but where date of initial ACC diagnosis is used instead of date of first infusion.

Time to Response (TTR): defined as the interval from the start of investigational product to the initial (subsequently confirmed) response of CR or PR (per RECIST v1.1 or modified MDA criteria), as determined by Investigator review. TTR will be calculated in months as $(\text{date of initial response/censoring} - \text{date of first infusion} + 1) / 30.4375$.

Patients without response will be right censored at their last tumor assessment.

As part of the sensitivity analysis, TTR will also be derived as follows:

- As above but where confirmation of PR/CR is not required.
- As above but based on central review rather than Investigator review.
- As above but based on central review rather than Investigator review and where confirmation of PR/CR is not required.

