7.5.3.1 Duration of Response

The Kaplan-Meier method will be used to analyze DOR. The Kaplan-Meier curves will be plotted. Counts and percentages for number of subjects who experienced the event of interest and those who are censored will be presented along with minimum and maximum duration in months. The median, 25th and 75th percentiles will be estimated and their corresponding Brookmeyer-Crowley 95% CIs using the Kaplan-Meier estimates. Landmark estimates will be provided for 2, 4, 6 and 8 months after start of investigational product.

The following sensitivity analyses will be conducted:

- The DOR analysis will be repeated using the PP analysis set;
- The DOR analysis will be repeated using unconfirmed response;
- The DOR analysis will be repeated using central read based on confirmed response;

□

The DOR analysis will be repeated using central read based on unconfirmed response.

Subgroup analyses will not be performed for DOR due to the small number of responders.

DOR will be displayed graphically by patient and cohort using swimmer plots.

7.5.3.2 *Progression Free Survival*

PFS will be summarized similarly to DOR using the Kaplan-Meier method and estimates will be presented along with Brookmeyer-Crowley 95% CIs. Appropriate landmark estimates will also be included.

The following sensitivity analyses will be conducted:

- The PFS analysis will be repeated using the PP analysis set;
- The PFS analysis will be repeated using central read;
- The PFS analysis will be repeated using the subset of subjects with a BOR of PR (BOR will be based on the Investigator results irrespective of confirmation; PFS will be based on the Investigator results).

Subgroup analyses will also be performed based on the main subgroups outlined above for ORR. Kaplan-Meier curves will be plotted for each subgroup.

7.5.3.3 *Overall Survival*

OS will be summarized similarly to DOR using the Kaplan-Meier method and estimates will be presented along with Brookmeyer-Crowley 95% CIs. Appropriate landmark estimates will also be included.

The following sensitivity analyses will be conducted:

- The OS analysis will be repeated using the PP analysis set;
- The OS analysis will be repeated using the Safety analysis set;
- The OS analysis will be repeated using the subset of subjects with a BOR of PR (BOR will be based on the Investigator results irrespective of confirmation).

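### If patients stop for undocumented progression, Table 7 censoring is likely to flatter PFS and DOR, and no planned sensitivity analysis changes that rule

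*SAP*

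**What the plan says.** SAP Section 6.4.1.2 defines PFS as "defined as the interval from the start of investigational product to the earlier of the first documentation of disease progression" or death. It fixes the censoring rules in one table for two endpoints: "For DOR (and PFS) the date of progression or death and censoring will be based on the Food and Drug Administration (FDA) guidance", as set out in Table 7.

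Three rows of Table 7 matter here:
- "Treatment discontinuation for undocumented progression": censored at the last disease assessment.
- Other anticancer treatment begun before documented progression or death: censored at the last assessment before that treatment.
- "Death or progression after more than one missed disease assessment": censored at the last progression-free assessment before the first missed visit.

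The sensitivity derivation listed for PFS in Section 6.4.1.2 is "As above but based on central review rather than Investigator review". SAP Section 7.5.3.2 adds "The PFS analysis will be repeated using the PP analysis set" and a repeat in patients whose best response was PR, and it restates the central-read repeat: "The PFS analysis will be repeated using central read". For DOR, Section 7.5.3.1 plans the PP set, unconfirmed response, and central read with and without confirmation.

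On follow-up imaging, the notes to the protocol's Schedule of Activities say that in long-term follow-up, "only in patients who discontinued investigational product due to toxicity, radiographic imaging will be done every 3 months until disease progression" or new therapy.

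**The concern.** Kaplan-Meier estimation treats a censored patient as having the same outlook as those still under observation. A patient taken off drug because the investigator judges the disease to be progressing has a worse outlook. Moving the censoring date back to the last assessment removes that patient just before the failure. A patient who switches to another anticancer drug may be in a similar position.

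The expected error is favourable to AL101. The study is non-comparative, so there is no control arm in which a similar error could partly cancel. PFS and DOR are secondary efficacy endpoints that will be read as absolute figures. A reader of the planned outputs would not see what either estimate becomes if these patients are counted as failures.

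**Working it through.** **1. Does any planned repeat change the rule?**

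| Repeat | What it changes | Censoring of clinical progression |
|---|---|---|
| PP set (PFS, DOR) | who is analysed | unchanged |
| Central read (PFS, DOR) | who reads the scans | unchanged; a progression that was never imaged cannot be read |
| Best response of PR (PFS) | who is analysed | unchanged |
| Unconfirmed response (DOR) | who counts as a responder | unchanged |

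**2. Can the event be recovered later?** Partly.
- Protocol Section 5 gives early discontinuers an EOS visit, and protocol Table 2 requires imaging there, 30 days after the last dose (±7). That scan can document some progressions.
- Post-treatment therapy is unrestricted (protocol Section 7.1.4). If new therapy starts before the EOS scan, Table 7 censors at the earlier assessment.
- After EOS, only patients who stopped for toxicity are imaged.
- A death between planned assessments is an event, but a death after more than one missed assessment is censored. Table 7 gives no order of precedence among its rows.

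**3. How large could the effect be?** The documents contain no PFS median, event count or rate of clinical-only progression, so there is no PFS figure to reproduce. From the documents: scans every 8 weeks (SAP 6.1), and an Efficacy Evaluable set that requires a post-baseline tumour assessment (SAP 7.2). Assumed: exponential PFS with a median m of 3.5 to 5.5 months, and a share f of progressions that remains undocumented after the EOS scan and any countable death. The 6-month landmark is illustrative; the SAP names no PFS landmarks.

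*Closed form.* The true hazard is ln 2/m. Censoring a share f leaves an estimated hazard of (1−f)·ln 2/m. The median is therefore multiplied by 1/(1−f), and 6-month PFS reads exp[−6(1−f)·ln 2/m]. For m = 5.5 and f = 20%, the true value is exp(−0.756) = 46.9%; the plan gives exp(−0.605) = 54.6%; the median reads 5.5/0.8 = 6.9 months.

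| f | Median multiplied by | 6-month PFS, m = 3.7 (true 32.5%) | 6-month PFS, m = 5.5 (true 46.9%) | Overstatement, points |
|---|---|---|---|---|
| 0% | 1.00 | 32.5% | 46.9% | 0 |
| 5% | 1.05 | 34.4% | 48.8% | about 2 |
| 10% | 1.11 | 36.4% | 50.6% | about 4 |
| 20% | 1.25 | 40.7% | 54.6% | about 8 |
| 30% | 1.43 | 45.5% | 58.9% | 12–13 |

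*Simulation on the 8-week scan grid* (medians 3.5 and 5.0). Documented progressions are dated at the next scan. Undocumented ones are censored at the previous scan (plan) or counted on their own date (alternative).

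When patients with no post-baseline assessment are excluded, as the Efficacy Evaluable set requires, the 6-month values under plan and alternative are:

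| f | m = 5.0 | m = 3.5 |
|---|---|---|
| 10% | 0.501 − 0.475 = 2.6 points | 0.363 − 0.340 = 2.3 points |
| 20% | 0.540 − 0.488 = 5.2 points | 0.417 − 0.362 = 5.5 points |
| 30% | 0.573 − 0.489 = 8.4 points | 0.447 − 0.354 = 9.3 points |

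At f = 5% the gap is about 1 point. The alternative column drifts with f because the exclusion removes early clinical failures. Without that exclusion the gaps are about 2, 3.5, 7.5 and 12 points for f of 5%, 10%, 20% and 30%.

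Taking both versions together gives 0, about 1–2, 2.5–4, 5–8 and 8–12 points. Medians on the scan grid jump by whole scan intervals (56/30.4375 = 1.84 months), so the landmark is the steadier measure.

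**The case against.** The strongest reply is that the rule is prespecified, is attributed to a cited FDA guidance, and keeps a subjective judgement out of the main estimate in an open-label trial. PFS is secondary and descriptive, with no test or decision threshold, and SAP Section 7.5.4.4 calls the study exploratory. All of that stands. It supports keeping Table 7 as primary; it does not replace a sensitivity analysis of its least neutral assumption.

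A reader might infer that PFS simply is biased upward and that nothing in the outputs would reveal it. The documents do not support that reading. They give no rate of clinical-only progression. The EOS scan and the death rows can recover some or all of these events. The SAP will also report discontinuation by primary reason and cohort (Section 7.3.1), numbers of events and censored patients (7.5.3.1, which PFS follows) and subject listings (7.1.1). A reader may therefore be able to bound how many patients are affected. What is missing is the count by Table 7 reason and the re-estimated curve.

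High values of f are also demanding. If the EOS scan caught half of the clinical progressions, f = 30% would require 60% of progressions to be clinical-only at discontinuation.

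**Conclusion.** The gap is real and modest. Table 7 censors discontinuation for undocumented progression, and the start of new anticancer therapy, at the last assessment; no planned PFS or DOR repeat changes this. If such patients occur and are not captured by the EOS scan or a countable death, the censoring is likely informative and both estimates are expected to be too high.

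The size is unknown. The simulated range for 6-month PFS runs from nothing at f = 0 to 8–12 points at f = 30%, and the closed form reaches 13 points with a 3.7-month median. These figures rest entirely on the assumed share, an exponential model and the assumed medians. They cover undocumented progression only; no separate size was calculated for new therapy or for DOR. The case is for one missing sensitivity analysis per endpoint plus a table, not for a different primary rule. ORR and OS do not use Table 7 and are unaffected.

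**What to change.** Keep Table 7 as the primary rule. Add to SAP Section 7.5.3.2 for PFS, and to 7.5.3.1 for DOR:
- (a) a sensitivity analysis that counts discontinuation for undocumented or clinical progression as an event on the discontinuation date;
- (b) a separate analysis that also counts the start of new anticancer therapy as an event on its start date;
- a table of patients by Table 7 censoring reason and cohort.

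Keeping (a) and (b) apart matters because (b) may count patients who switched, for example after toxicity, without progressing. Pooling the two would hide how much comes from clinical progression.

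The programming cost is small: two further Kaplan-Meier runs per endpoint and one table. The identification cost may be larger. The discontinuation reasons in protocol Section 4.5 include treatment failure, investigator request and other, but no separate clinical-progression category, so a medical review of reasons may be needed before database lock. Clinical progression is also subjective in an open-label trial, so these analyses should stay supportive. Their estimates will look less favourable than the primary ones if any such patients exist.

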### **9.6 EFFICACY**

#### **9.6.1 Definition of Efficacy Endpoints**

The primary efficacy endpoint is the objective response rate (ORR). ORR is defined as the proportion of patients who have a best overall response (BOR) of CR or PR as determined using RECIST v1.1 or modified MDA criteria for bone-exclusive disease (see [Table 11](#)). BOR is defined as the best response recorded between the date of first dose of investigational product and the date of subsequent anti-cancer therapy. A BOR of CR or PR requires confirmation of the assessment at least 4 weeks later.

Other efficacy endpoints are as follows:

Confidential

Document State: Effective (Controlled)  
CONFIDENTIAL

Page 83 of 118

- DOR, defined as the interval from the first documentation of CR or PR to the earlier of the first documentation of disease progression (per RECIST v1.1) or death from any cause.
- PFS, defined as the interval from the start of investigational product to the earlier of the first documentation of disease progression or death from any cause
- OS, defined as the time from the date of start of treatment to the date of death from any cause. Patients who are lost to follow-up and those not known to have died by the cut-off date for analysis will be censored on the date the patient was last known alive, or the data cut-off date, whichever is earlier.

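### Registry searches extend overall survival follow-up only for withdrawn patients found dead, so censoring depends on outcome; separately, the SAP's OS definition omits the protocol's data cut-off

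*SAP*

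**What the plan says.** SAP 6.4.1.2 builds the OS definition from three rules.

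- Default: "Subjects with no documentation of death will be censored at the last date known to be alive, per the data collection".
- Search: "Sites will be asked to search public registries for any possible death dates for subjects who withdrew consent from the study".
- Use of the result: "Where it is possible for this search to be done, any deaths found will be included in the analysis".

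Nothing says what happens to a searched patient for whom no death is found. Under protocol section 5 the three-monthly survival calls end when consent is withdrawn, so the default rule leaves that patient censored at about the time of withdrawal. SAP 7.5.4.2 confirms that consent to survival follow-up can be withdrawn.

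Protocol 9.6.1 has no registry step. It censors patients lost to follow-up or not known dead by the cut-off, and it caps the date: they "will be censored on the date the patient was last known alive, or the data cut-off date, whichever is earlier". The SAP's OS text has no cap. The only date in the SAP's endpoint definitions is in Table 7, which is titled for PFS and DOR: "All patients still alive and without documentation of disease will be censored as of July 31, 2022".

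On method, SAP 7.5.3.3 states: "OS will be summarized similarly to DOR using the Kaplan-Meier method". SAP section 4 gives the SAP precedence over the protocol. SAP 7.10 lists only the addition of disease control rate and time to response as changes.

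**The concern.** Kaplan-Meier estimation assumes that, at any time, patients who are censored have the same prospects as those still followed. The SAP's rule breaks this by construction. Suppose a patient withdraws at month 6. If a registry shows death at month 20, the patient counts as at risk until month 20 and as an event. If the patient is searched and not found dead, follow-up ends at month 6. After withdrawal, deaths enter the numerator while the survivors' time at risk is missing from the denominator.

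At stake are the OS median, quartiles, landmark estimates and their intervals. The same rule feeds the per-protocol, Safety-set, partial-responder, subgroup and alternative-time-origin OS analyses in SAP 7.5.3.3. None of these removes the registry information, so the effect would not show in any planned sensitivity analysis.

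The missing cut-off is a second, separate gap. No stated OS rule keeps out deaths or contacts recorded after the data cut.

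**Working it through.** **Inputs.** The documents state no OS assumption, withdrawal rate or registry coverage, so there is no plan figure to reproduce. The following are assumptions.

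- Exponential OS, with true 24-month OS of 39.7% or 50.0% in step 1 and true medians of 12, 24 and 36 months in step 2.
- 10, 20 or 30% of patients assigned a withdrawal time within the first 12 months. At 20% with a median of 24 months, about 17% actually withdraw before death.
- Coverage: the share of withdrawn patients for whom a complete search is possible.
- Hazard ratio (HR) after withdrawal: 1 means that withdrawal is unrelated to survival.

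**Estimator.** S(t) is the product over death times up to t of (1 − d/n), with d deaths among n at risk. Under the SAP's rule, d includes every registry death after withdrawal, while n omits the searched patients not found dead.

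**Step 1: full capture, HR 1** (87 patients, 24-month accrual, cut-off at month 36, 1,500 trials per setting). Estimated 24-month OS under the SAP's rule:

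| True value | 10% withdrawal | 20% | 30% |
|---|---|---|---|
| 39.7% | 37.7 | 35.5 | 33.5 |
| 50.0% | 48.1 | 45.8 | 43.1 |

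The falls are 39.7 − 37.7 = 2.0, then 4.2 and 6.2 points; and 50.0 − 48.1 = 1.9, then 4.2 and 6.9 points. A re-run under the same assumptions kept both the no-search rule and the symmetric rule (searched patients with no death found are censored at the cut-off) within 0.4 points of the truth.

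**Step 2: vary coverage and HR** (large-sample runs, cut-off 18 to 42 months after first dose, 20% assigned withdrawal). With HR 1 and true medians of 12 to 36 months, 24-month OS falls by 0.7 to 1.0 points at 25% coverage, 1.3 to 1.9 at 50%, and 2.4 to 3.7 at 100%. At full coverage a true median of 24.0 months is estimated as 21.8, and one of 36.0 as 31.2.

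Net bias in 24-month OS under the SAP's rule, in points, true median before any withdrawal effect 24 months:

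| HR after withdrawal | 0% coverage (no search) | 25% | 50% | 75% | 100% |
|---|---|---|---|---|---|
| 1 | 0.0 | −0.9 | −1.9 | −2.8 | −3.7 |
| 1.5 | +2.2 | +0.9 | −0.4 | −1.6 | −2.7 |
| 2 | +4.0 | +2.3 | +0.8 | −0.7 | −2.0 |
| 3 | +6.3 | +4.2 | +2.3 | +0.5 | −1.1 |

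In every setting with some coverage, the SAP's rule gave a lower estimate than the symmetric rule applied to the same search. With HR 2 and 50% coverage, for example, the truth is 46.0%, the SAP's rule gives 46.8% and the symmetric rule 47.9%.

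**Step 3: the cut-off alone** (no withdrawals, calls every 3 months, data extracted 6 months after the cut-off, true median 24 months). True 36-month OS is 0.5^(36/24) = 35.4%.

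- Protocol rule with cut-off: 32.9%.
- No cut-off, calls continue: 34.1%.
- No cut-off, calls stop but later deaths still enter: 27.0%.

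Omitting the cut-off can raise or lower the estimate. The protocol rule is itself 35.4 − 32.9 = 2.5 points low here, because survivors are censored at their last call while deaths count up to the cut-off.

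**The case against.** The strongest case against has five parts.

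1. **Direction.** A reader might infer that this trial's OS will be biased downward. The documents do not support that, because they give neither coverage nor any information on who withdraws. If sicker patients leave and searches are partial, the net bias is upward: +0.8 points at HR 2 and 50% coverage. This stands. What remains is the downward push relative to symmetric use of the same search.

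2. **The search may help.** A reader might also infer that OS without any search would be unbiased. That holds only if withdrawal is unrelated to survival. In the table, at HR 2 or 3 the SAP's rule is nearer the truth than no search at every coverage shown; at HR 1.5 and full coverage it is not (−2.7 against +2.2). The SAP cites FDA guidance for the search, and nothing here opposes searching. The objection is to using only half of the result.

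3. **The cut-off.** It is tempting to treat the missing cut-off as part of the downward bias. Step 3 shows that it is not, and restoring it would not cure the asymmetry, since the protocol also censors at last known alive. One can argue that the protocol's cap still applies where the SAP is silent. But the SAP restates the censoring date without the cap and claims precedence, so the text is ambiguous at best.

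4. **The obvious repair can overshoot.** Absence from a death registry is not proof of life. If every withdrawn patient is searched but half of the deaths are missed, the symmetric rule gives 53.3% against a true 49.8%. This stands and limits the fix.

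5. **Importance.** OS is secondary and descriptive, each cohort is analysed separately, and at n = 42 the sampling SD of 24-month OS is about 8.7 points under the accrual and cut-off of step 1 (1.96 × 8.7 ≈ 17 either side). This bounds the consequence. It does not justify a stated rule that ties censoring to outcome when the repair is cheap.

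**Conclusion.** The concern holds in limited form. The SAP's OS rule extends follow-up after consent withdrawal only for patients found dead, which violates the Kaplan-Meier censoring assumption and lowers OS relative to symmetric use of the same search. The size is about 2, 4 and 6 to 7 points of 24-month OS at 10, 20 and 30% withdrawal. That rests on full registry capture, withdrawal within the first year unrelated to survival, and exponential OS. It is about half as large at 50% coverage. The net bias in this trial cannot be signed from the documents.

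Independently, the SAP's OS definition lacks the data cut-off of protocol 9.6.1, with effect in either direction. Neither the registry step nor the loss of the cut-off appears in SAP 7.10. The objective response rate, which carries the sample size and the primary analysis, is untouched.

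**What to change.** In SAP 6.4.1.2 and 7.10:

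1. State one OS data cut-off for all patients, and ignore deaths and contacts after it.
2. Record the search date, the registry and the result for each withdrawn patient.
3. Use the result only where the registry is judged complete for that patient: a death on or before the cut-off is an event; otherwise censor at the earlier of search date and cut-off. Censor all other withdrawn patients at the last date known alive before withdrawal, whatever a search found.
4. Report OS without any registry information as a sensitivity analysis.
5. List the registry step and the cut-off rule in SAP 7.10 as changes from the protocol.

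The cost is a few sentences, a short record per search and one further OS run. Two downsides remain. An incomplete registry wrongly judged complete would overstate OS, which the analysis without registry data helps to expose. Setting aside deaths found in incomplete registries gives up some information and, if withdrawn patients do worse, leaves OS too high for that group; the report should say so.
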